## 7.5 Statistical methods

### 7.5.1 Analysis population

Analysis of the primary and secondary outcomes are based on the full analysis set (FAS). Further, the analysis of the primary outcome will be performed in the per-protocol set (PPS) to evaluate the treatment effect for patients with good protocol adherence, if FAS and PPS comprise a sufficiently different set of patients. For safety analysis, adverse events and SAEs will be analyzed descriptively.

The FAS includes all patients who were randomized. Every attempt will be made to acquire missing data for the primary outcome.

The PPS includes all patients of the FAS without serious violations against the study protocol. The following protocol violations will be classified as serious:

- At least one inclusion or exclusion criterion was not met.
- Treatment was not conducted as mandated, that is:
  - Temporal delay of at least one treatment session by 2 weeks of the planned date (based on the date of the first treatment session)

- Absence of more than 6 of the planned 12 treatment sessions
- Intake of forbidden medications
- Psychological treatment during study participation

Further serious protocol violations will be specified in the data analytic plan, if necessary.

### 7.5.2 Planned methods for analysis

Primary analysis: The primary endpoint, the number of OBEs at post-treatment (t1) ~~and pre-treatment (t0)~~, will be investigated using ANCOVA with OBEs at t1 as the dependent variable, OBEs at t0 as a covariate as well as the stratification criteria. A closed-testing procedure will be used, meaning that the initial comparison will be between the two intervention groups combined and the waiting group and the three pair-wise tests (~~fNIRS vs. waiting group, EEG vs. waiting group and fNIRS vs. EEG~~) will be performed without adjustment if the global test is significant. The analysis will follow the intent-to-treat principle and will be based on the full analysis set. Every attempt will be made to acquire missing data. If data missing for the primary outcome can be expected to bias results in a meaningful way, multiple imputation will be performed. Further, the analysis of the primary outcome will be performed in the per-protocol set to evaluate the treatment effect for patients with good protocol adherence.

Secondary analyses: Recruitment and attrition rates will be described quantitatively and a qualitative analysis of the hurdles involved in recruitment and in maintaining patient commitment will be presented. Further secondary outcomes will be analyzed in an exploratory, descriptive manner, and will be evaluated presented with 95% CIs, as well as parametric or non-parametric tests, depending on the scale level and type of distribution of the observed variables. Multiple comparisons given three arms will be taken into account using e.g. Dunnett's test or Tukey's Honest Significant Differences and where all pair-wise comparisons will be made, independent of the result of a global test. Maintenance of treatment success over time will be evaluated. Predictors of treatment outcome will be identified using regression analyses.

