Intervention. *fNIRS neurofeedback:* The fNIRS neurofeedback training will be delivered in 12 individual sessions (60 min) over 8 weeks. Personally salient binge food stimuli (and matched neutral stimuli, i.e., household items) will be pre-selected from validated databases. The fNIRS neurofeedback protocol will include a *localization trial* at the outset, during which the individual target area in the prefrontal cortex (e.g., dorsolateral, orbitofrontal) that demonstrates reliable activation differences in response to food stimuli compared to rest, will be selected for training (region of interest, ROI). Detailed working instructions will be derived from pilot measurements. The localization trial will include a rest period, a perceptual food cue exposure (“watch”), a craving food cue exposure (“allow yourself to crave”), and a perceptual neutral cue exposure (household items). The *neurofeedback trials* will include a rest period and regulation food cue exposure (“reduce craving”), followed by rest and reinforcement. During food cue exposure, each food cue

is presented with variable size according to the change in percent blood oxygenation level dependent signal, relative to the preceding fixation block. The goal is to reduce craving by decreasing the size of the food cue. For optimal learning, cognitive-behavioral techniques will be used such as information, reinforcement and self-reinforcement, guided discovery of self-regulation skills, cognitive restructuring, goal setting and planning of transfer into daily life, and homework assignments.

Control. Two control conditions will be used: (1) *EEG neurofeedback*: A validated food cue-based EEG training protocol (high beta training) will be used with 12 individual sessions (60 min) over 8 weeks. This condition serves to examine the comparative efficacy and specificity of changes. (2) *Delayed treatment control condition*: The untreated group will not receive any treatment over 8 weeks, but will afterwards be offered fNIRS neurofeedback. This control condition is essential for examining basic efficacy.

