### 7.4.3 Drop-outs

A drop-out rate of 15% was observed in an EEG neurofeedback trial with a follow-up 3 months after end of treatment. Based on these data and our own experience we assume a dropout rate of 20%. Although dropped-out from treatment, patients who discontinued treatment will be assessed at later assessment time points, if possible.

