## 3 General analysis definitions

### 3.1 Analysis populations

Analysis of the primary and secondary outcomes are based on the full analysis set (FAS). Note that patients fulfilling the criterion for abstinence at T0 will not be included in the analysis for this endpoint. Further, the analysis of the primary outcome will be performed in the per-protocol set (PPS) to evaluate the treatment effect for patients with good protocol adherence, if FAS and PPS comprise a sufficiently different set of patients. Analysis of the fNIRS data will be performed in the fNIRS data set.

The FAS includes all randomized patients unless purely technical issues precluded the fNIRS measurements. In particular, three patients had to be replaced because of the aforementioned technical issues with fNIRS. Patients who could not complete the intervention due to the SARS-CoV-2 situation will be retained in the FAS if they completed at least 5 sessions and provided OBE data at T1. In control patients, those who could not attend T0WL due to SARS-CoV-2 will not be retained in the FAS.

The PPS includes all patients of the FAS without serious violations of the study protocol. The following protocol violations are classified as serious:

- Violation of at least one inclusion or exclusion criterion

- Treatment was not conducted as mandated, that is
  - Temporal delay of last attended treatment session by 4 weeks relative to the planned date, `exdat`, (based on the date of the first treatment session). Note that consideration of a maximum of two weeks' delay in each session as originally foreseen was not considered feasible.
  - Absence of more than 6 of the planned 12 treatment sessions (based on `meet`)
- Use of forbidden medication
- Psychological treatment during study participation (was not the case, otherwise it would be documented in the "comments")

The fNIRS/EEG data set includes all patients from the fNIRS/EEG group of the FAS who provided data for more than a single neurofeedback session. Participants with fewer sessions are excluded from the analyses, because the definition of neurofeedback *training* does not apply for these participants and there is no information on between-session variability.

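### The per-protocol analysis is meant to give the effect in adherent patients, but before the endpoint only the neurofeedback arms can be selected on attendance, so its contrasts with the waitlist do not estimate that effect

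*Protocol*

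**What the plan says.** Protocol 7.5.2 puts the primary analysis in the full analysis set (FAS) and adds that it "will be performed in the per-protocol set to evaluate the treatment effect for patients with good protocol adherence". Protocol 7.5.1 and SAP 3.1 make this second analysis conditional: it is run "if FAS and PPS comprise a sufficiently different set of patients". No threshold is given.

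The per-protocol set (PPS) is the FAS without serious violations. Two of the criteria concern how treatment was delivered:

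- Attendance, the same in both documents: "Absence of more than 6 of the planned 12 treatment sessions" (Protocol 7.5.1). A patient with 6 or more sessions stays in.
- Timing, which differs. Protocol 7.5.1 has "Temporal delay of at least one treatment session by 2 weeks of the planned date". SAP 3.1 has "Temporal delay of last attended treatment session by 4 weeks relative to the planned date" and explains that the stricter rule was not feasible.

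The other criteria can apply in any arm: eligibility ("At least one inclusion or exclusion criterion was not met"), forbidden medication, and psychological treatment during the study, which the SAP says did not occur.

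On the waitlist, Protocol 1.2.1 states: "The untreated group will not receive any treatment over 8 weeks". SAP 2.1 takes the waitlist endpoint at T0WL, the visit after the waiting period, and SAP 2.2 places that arm's fNIRS course after T0WL.

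**The concern.** An analysis of the effect in adherent patients has to compare treated adherent patients with untreated patients who would have adhered. At T0WL nobody knows which waitlist patients those are. The PPS removes poor attenders from fNIRS and EEG and leaves their counterparts in the waitlist.

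If poor attenders tend to have more binge-eating episodes for reasons unrelated to treatment, the treated PPS is the better-prognosis part of its arm, while the waitlist is a mixture. The ANCOVA adjusts for baseline episodes and the stratification factors. It cannot remove a difference in prognosis that goes beyond those variables.

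This touches the leading contrast (both neurofeedback arms against waiting) and both pairwise contrasts with the waitlist. In fNIRS versus EEG both arms are filtered, though attendance may still differ between them. At stake is the reading of the only analysis that the plan assigns to adherence: a reader would take a larger PPS effect as evidence that neurofeedback works when taken as intended.

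**Working it through.** The documents give no figure for the PPS result or for the share of patients it excludes, so there is no plan figure to reproduce.

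**Inputs.**
- 26 patients per arm, so 52 treated and 26 waiting (Protocol 7.4.4).
- Adherent-patient effect of -0.55 SD, the planning effect (Protocol 7.4.4).
- Share excluded q = 0.20. This is a proxy: Protocol 7.4.3 says "we assume a dropout rate of 20" per cent, but about drop-out, not about missed sessions.
- Prognosis gap g of 0.3, 0.5 or 1.0 SD: how much higher the untreated outcome of poor attenders is. This is an assumption; the documents give no value.

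**Bias of the PPS contrast.** Take the adherent untreated mean as 0. The waitlist mean is q × g. The treated PPS mean is the true effect. The contrast is therefore the true effect minus q × g.

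| g (SD) | q × g | Simulated bias, true effect 0 | Two-sided rejection | Simulated PPS estimate, true effect -0.55 |
|---|---|---|---|---|
| 0.3 | 0.2 × 0.3 = 0.06 | -0.064 | 5.6% | -0.612 |
| 0.5 | 0.2 × 0.5 = 0.10 | -0.100 | 6.9% | -0.646 |
| 1.0 | 0.2 × 1.0 = 0.20 | -0.190 | 13.3% | -0.739 |

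Simulation used 6,000 runs per cell. Against -0.55 the PPS overstates the effect by 11% (0.612/0.55), 17% (0.646/0.55) and 34% (0.739/0.55).

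**Second model.** The planned type of ANCOVA was simulated with an assumed baseline-outcome correlation of 0.5 and a correlation rho between attendance and the baseline-adjusted outcome (4,000 runs). With 20% excluded from the treated arms only and a true effect of 0:
- rho 0.2: bias -0.06 SD, rejection 6.2%
- rho 0.3: bias -0.09 SD, rejection 7.3%
- rho 0.5: bias -0.16 SD, rejection 11.6%

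With rho = 0, or with the same selection in both arms, bias is about 0 and rejection stays at 4.6-5.5% across exclusion shares of 20-40%. The distortion therefore needs both a prognostic attendance and selection confined to the treated arms.

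**Alternative: complier average causal effect (CACE).** Waitlist patients have no access to neurofeedback before T0WL, so non-attendance is one-sided, and CACE = intention-to-treat difference / proportion attending. If non-attenders receive a fraction r of the effect, the intention-to-treat difference is -0.55 × (0.8 + 0.2r), and

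CACE = -0.55 × (0.8 + 0.2r)/0.8 = -0.55 × (1 + 0.25r).

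- r = 0: -0.55 (simulated -0.546 to -0.553; null rejection 5.2-5.3%)
- r = 0.25: -0.58
- r = 0.5: -0.62
- r = 1: -0.69

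The CACE error is 0.55 × 0.25r = 0.1375r and the PPS error is 0.2g. CACE is closer when r < 0.2g/0.1375, which is r < 0.44 for g = 0.3 and r < 0.73 for g = 0.5. At g = 1.0 it is closer for every r up to 1.

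**The case against.** **Selection by arm is not written down.** The session criteria apply to FAS patients without limit by arm or time, and waitlist patients later have a 12-session fNIRS course whose attendance will be known at the final analysis. On a literal reading, poor attenders leave all arms, and equal selection gives no bias. It stands that the text is silent. But excluding waitlist patients for sessions after T0WL selects on behaviour that follows their endpoint and may depend on it, so equal selection cannot be presumed.

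**The direction is not established.** Nothing in the documents shows that poor attenders do worse. Patients who improve early and stop coming would reverse the sign, and purely logistical delays would give no bias. This stands: the direction is conditional. At the mildest gap examined, rejection is 5.6%, close to nominal.

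**The complier estimate can err the same way.** This also stands. If late but full attenders were classed as non-adherent, r could approach 1 and the estimate -0.69. The variable to instrument must therefore be attendance alone.

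**Readings that go too far.** A reader might infer that good attenders are compared with all waitlist patients. They are not: eligibility and medication criteria filter that arm too. A reader might also infer that a favourable PPS result could rescue a failed primary test. Nothing in the plan allows this: inference rests on the FAS, the PPS analysis is supportive and conditional, and under SAP 4.1 a non-significant global test ends formal testing.

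**Conclusion.** The point holds in a limited form. As defined, the PPS contrasts with the waitlist do not estimate the effect in patients with good adherence, because adherence before the endpoint can be observed only in the treated arms and the ANCOVA covariates do not make up for that.

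With an assumed 20% excluded and gaps of 0.3 to 1.0 SD, a null effect appears as about -0.06 to -0.19 SD in favour of neurofeedback, with two-sided rejection of about 6-13%. These figures rest on the proxy exclusion share, on poor attenders having the worse prognosis beyond baseline episodes and strata, and on normally distributed outcomes. If attendance is not prognostic, there is no bias. An unconditional statement that the analysis favours neurofeedback is not supported.

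The primary conclusion is untouched by this point. What changes is the claim that may be made about adherent patients, and the correction is inexpensive.

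**What to change.** In Protocol 7.5.1 and 7.5.2 and SAP 3.1 and 4.1:

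1. Label the PPS result descriptive and drop the statement that it evaluates the effect in adherent patients.
2. State that waitlist patients are not excluded for sessions after T0WL.
3. Add a CACE as the supportive adherence analysis for pooled neurofeedback versus waiting. Randomised arm is the instrument for attending at least 6 of 12 sessions; baseline episodes, stratification factors and imputations are as in the primary analysis. Use all randomised patients, as Protocol 7.5.1 defines the FAS; SAP 3.1 is narrower and partly depends on session counts.
4. Treat session timing as a sensitivity analysis only, and report the CACE over a range of residual effects in patients with fewer than 6 sessions.

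The cost is one two-stage model and a few sentences. The interval is wider (standard error about 0.30 against 0.25 SD), the main estimate assumes that patients with fewer than 6 sessions gain little, and the analysis does not address fNIRS versus EEG.

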## 7.6 Statistical monitoring

The structure of the trial is fairly simple, i.e. there are a small number of visits at which primarily psychological measures will be obtained, often questionnaires and structured interviews. As such, statistical monitoring will focus on a small number of key issues, including

- missing data
- drop-outs and the proportion in each arm
- timing of visits
- number and timing of therapy sessions.

## 7.7 Interim analysis

No interim analysis will be performed.

## 7.8 Final analysis

The final analysis will be performed after the last patient has terminated the trial, all database queries have been resolved and the database has been locked.

---

## 8 ETHICAL CONSIDERATIONS

### 8.1 GCP-declaration

The trial will be conducted in accordance with the guidelines for Good Clinical Practice (GCP). All involved parties of the study (principal investigator, study and data management, study team) commit themselves to the Declaration of Helsinki (Version Somerset West 1996), as well as all pertinent national laws and the ICH Guideline for Good Clinical Practice (GCP) E6 issued in June 1996 and CPMP/ICH/ 135/95 from September 1997.

### 8.2 Ethical approval

According to the specifications of §15 of the German federal Medical Association's professional code of conduct, ethical approval of the study will be sought at the responsible ethics committee (Ethics Committee of the University of Leipzig).

### 8.3 Supplementary changes of the study protocol

Changes in the study protocol must be reported to the Ethics Committee of the University of Leipzig and, where necessary, a new vote has to be gathered. Changes needing a positive vote may only be realized after the Ethics Committee of the University of Leipzig agreed with these changes.

Changes that require the vote of the Ethics Committee of the University of Leipzig are associated with one or more of the following aspects:

- Essential changes in treatments
- Reappraisal of patient risks
- Additional assessments or analyses that warrant changes of the patient education and consent form
- Changes that affect the management and conduct of the study substantially.

## 9 DOCUMENTATION

### 9.1 Patient identification list

All patient-related data will be documented in a pseudonymized format. Therefore, a pseudonym will be used with which the patient's identity cannot be inferred from alone. The assessor keeps a patient identification list (PIL) which includes the patient identification number, the patient's name and birth date. The PIL must be treated with absolute confidentiality, must not leave the study center and has to be archived for at least 10 years after the end of the study. In addition, the patient's participation in the study must be documented in the patient's record.

### 9.2 Case Report Forms (CRF)

Case report forms (CRF) will be designed by the ZKS data management in close cooperation with the study group.

The CRF for collection the clinical data will be provide to the trial center as electronic form (eCRF). Authorized members of the study team for this task will connect to the database via internet and input

data directly into the SecuTrial database via eCRF data entry masks. In order to facilitate the documentation as per protocol in case of malfunction of the electronic system or any of its components, a paper version of the clinical CRF will be additionally provided. The content of this paper version will be transferred to the eCRF as soon as the electronic system is available again. The eCRF will be completed shortly after each study visit.

Each CRF page of the clinical part will be signed electronically by an authorized member of the study group. This confirms that all data on the eCRF are correct and have not been changed. If a value gets changed on the eCRF later the eCRF has to be signed again. This ensures that changes on the eCRF will be dated and signed as well. All entries and data changes will be tracked automatically including date, time and person who entered/changed information (audit trail). Corrections and major missing data have to be explained.

If the investigator authorizes other members of the study team to enter and sign CRF data, their name, initials, position, signature must be documented via Staff Signature und Delegation Log.

However, the investigator has final responsibility at all times for the accuracy and authenticity of all clinical and laboratory data entered in the CRF.

The psychological measures are provided to the trial center as a copy template. The ZKS Leipzig data management receives the original CRF, while the trial center is in charge to make a copy of the CRF which remains at the trial center. These will be entered into the eCRF by ZKS Leipzig staff afterwards.

Documentation at the paper-based CRF must be performed using a dark pen. For corrections, the incorrect data entry must be crossed out using a horizontal line so that the initial entry remains visible. The correction must be confirmed by initials and current date by authorized study staff. It is not allowed to use correction fluids.

Signature at the CRF confirms the correctness of data and possible corrections.

After the t1 diagnostic session (8 or 16 weeks after randomization, respectively), all original CRFs will immediately be sent to the ZKS Leipzig data management or collected by the monitor for data entry and analysis. Similarly, CRFs of the t2 follow-up visits (6 months after end of treatment) will be promptly sent to the ZKS Leipzig data management or collected by the monitor.

All data which are provided in the patient record are considered as source data.

### 9.3 Data management

All study data will be collected in the Clinical Data Management System (CDMS). The EDC Tool SecuTrial by InterActive will be used. The database will be validated according to the Standard Operating Procedures (SOPs) of the ZKS Leipzig - KKS prior to data capture.

The information entered into the database by the data management team of the ZKS Leipzig is systematically checked for completeness, consistency and plausibility by routines implemented in the CDMS. Error messages generated by these routines will be checked by the data management staff. Queries obviously not representing a problem will be closed. Errors with an obvious solution will be corrected by the staff of the ZKS Leipzig immediately (self-evident correction).

Discrepancies, errors or omissions will be passed to the investigator or an authorized member of the study team at the investigational site by the CDMS. The investigator will receive notification of all queries concerning his/her investigational site. The ZKS Leipzig will supervise and support the solution of the queries. Corrected data will be re-checked by automatic routines after entry. In case a query cannot be solved or closed by the investigator or designated study staff, the data management staff of the ZKS Leipzig may close the query. This shall happen in agreement with the study biometrician and

clarification, if the information addressed by the query is relevant for the results of the study, or not.

During the whole course of the study, a backup of all data is made on a daily basis. Unauthorized access to patient data is prevented by the access concept of the CDMS which is based on a strict hierarchy and role model. Any change of data (e.g. when data is changed in the CDMS during query management) is recorded automatically via audit trail within the CDMS.

At the end of the study, once all data in the CDMS have been declared complete and accurate, the trial will be locked in the CDMS. Thereafter, any changes to the data are possible only by joint written agreement between coordinating investigator, biometrician and data manager.

